# 7. ANALYSIS SET

# 7.1 All Enrolled Set

All screened subjects who provide informed consent, receive a subject ID, and provide demographic and/or baseline screening assessments, and are randomized in the study.

Demography and baseline characteristics tables as well as subject listings will be produced on the All Enrolled Set.

# 7.2 Exposed Set

All subjects in the All Enrolled Set who are randomized and received study vaccination.

# 7.3 Full Analysis Set (FAS) Immunogenicity Set

All subjects in the Exposed Set who are randomized, received study vaccination and provided immunogenicity data on Day 1 and Day 29 assessment.

In case of vaccination error, subjects in the FAS sets will be analyzed "as-treated" (i.e., according to the vaccine the subject received).

If a subject is unblinded before the completion of the Day 29 visit, he/she will be included in the FAS, but excluded from the Per Protocol.Set.

# 7.4 Per Protocol Set (PPS) Immunogenicity

All subjects in the FAS Immunogenicity who:

- Correctly receive the vaccine (i.e., receive the vaccine to which the subject is randomized within the defined window).
- Have immunogenicity assessments within the window of -7 to +21 days around the Day 29 visit, and Day 1 sample taken
- Have no protocol deviations leading to exclusion as defined prior to unblinding / analysis.
- Are not excluded due to other reasons defined prior to unblinding or analysis.

If a subject receives a vaccine, labelled for another subject but the same as the one the subject was randomized to, the subject will not be removed from the PPS. If a subject is unblinded during the study (except for SUSAR), he/she will be excluded from the PPS.

# 7.5 Safety Set

Subjects will be analyzed as "treated" (i.e., according to the vaccine a subject received, rather than the vaccine to which the subject may have been randomized).

### **Solicited Safety Set**

All subjects in the Exposed Set with any solicited adverse event data including body temperature measurements or use of analgesics/antipyretics recorded by the subject in the eDiary.

The investigator assessment of the solicited adverse event will be based on the subjects with nonmissing data recorded on the investigator assessment. In case, there are subjects without any eDiary data recorded (so not part of the solicited safety set) but with an investigator assessment an extra set will be defined for the investigator evaluation – **Solicited Safety Set, per investigator**.

# Unsolicited Safety Set (unsolicited adverse events)

All subjects in the Exposed Set for whom safety has been assessed after vaccination (including 30-minute post-vaccination assessment).

# **Overall Safety Set**

All subjects who are in the Solicited Safety Set and/or in the Unsolicited Safety Set.

# 7.5.1 Restricted Safety Set

Not applicable.

# 7.6 Other Analysis Set

Source Document #: SOP-00092497

For the analysis of the immunogenicity data collected at Day 181 assessment, revised sets of the FAS and PPS, Day 181 immunogenicity will be used. For the FAS, Day 181, subjects will be

26 Augustus 2021 Final Version 2.0

only included if there were Day 1 and Day 181 immunogenicity data collected. The PPS, Day 181 will be a subset of the FAS, Day 181 with a sample visit within +/- 4 weeks around the target Day 181 and excluding protocol deviations related to the subjects and no disallowed concomitant medication impacting the results was used.

### 8. GENERAL ISSUES FOR STATISTICAL ANALYSES

### 8.1 Adjustment for Covariates

The log-transformed antibody titers at Day 29 and Day 181 will be analyzed using an Analysis of Covariance (ANCOVA) model which includes the log-transformed pre-vaccination antibody titer, age subgroup stratification ( $\geq$ 50 – 64,  $\geq$ 65 years) and previous vaccination history stratification (no in previous 3 years, yes). Summary tables will show both adjusted and unadjusted GMTs for each vaccine group and adjusted and unadjusted GMT ratio for the different aQIVc investigational vaccines versus QIVc vaccine.

Instead of Vaccine group as categorical variable, levels of antigen and the amount of MF-59 will be included as covariates to model the antibody titers at Day 29 as function of the level of antigen and the amount of MF-59.

The main analysis of binary immunogenicity endpoints ((i.e., percentages of subjects with seroconversion and with titer  $\geq$ 1:40) will not be adjusted for any of the covariates. Binary data will be summarized for each group using unadjusted estimates and will be reported together with two-sided exact 95% CIs. Additional adjusted analysis may be done including the stratification factors age and previous vaccination history as covariates in a generalized linear model.

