## 8.1.1.1 Primary Immunogenicity Endpoints

Humoral immune response of the aQIVc formulations in comparison with the QIVc vaccine in terms of HI antibody response against homologous vaccine strains:

- Geometric Mean Titer (GMT): Geometric mean of HI antibodies at Day 1 and Day 29.
- Geometric Mean Fold Increase (GMFI): The Geometric mean of the fold increase in serum HI titer post-vaccination (Day 29) compared to pre-vaccination (Day 1).
- Percentages of subjects with HI titers  $\geq$  1:40 at Day 1 and Day 29.
- Percentage of subjects with seroconversion (defined as a ≥4-fold increase in titer postvaccination in those with pre-vaccination titer above the LLOQ (1:10), or a postvaccination titer ≥1:40 for subjects with baseline titer below the LLOQ (1:10) for HI antibodies at Day 29).

Note that the HI assay could be replaced by the MN assay due to a lack of agglutination.

Derived variables at Day 29:

- The GMT ratio (aQIVc formulation/QIVc) for each strain.
- The inter-group difference in the SCRs (aQIVc formulation minus QIVc) for each strain.

• The inter-group difference in the percentage of subjects with HI titer ≥1:40 (aQIVc formulation minus QIVc) for each strain.

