The binary endpoints (i.e. seroconversion or titer  $\geq$ 1:40) at Day 29 from each aQIVc formulation versus QIVc will be compared using the Miettinen and Nurminen method without adjustment for the age stratum. Each of the four strains will be analyzed separately. Additional exploratory analysis will be done including antigen and MF59 levels and adjustment for age and previous vaccination history using a generalized linear model for binary data.

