# 5. SAMPLE SIZE AND POWER CONSIDERATIONS

This study is an exploratory Phase 2 study without any formal hypothesis testing. The total sample size of 800 subjects has been determined based on feasibility and to provide information for further development. The power calculations are provided to illustrate what differences can be detected.

Anticipating 5% of the subjects will be non-evaluable over the course of the study (due to being lost to follow-up, having insufficient samples, incomplete laboratory results, or protocol violations, etc.), approximately 95 evaluable older adult subjects for each vaccine group will be included in the statistical analysis. Based on data from Seqirus study V133\_01EXP (Otten et al. 2020), it is assumed that the within group standard deviations for the log10 HI titers for all strains are about 0.7 or lower.

Assuming a standard deviation (SD) of 0.7 for the log 10 HI titer at Day 29, a comparison between dose groups with n=95 per group has at least 80% power with a two-sided  $\alpha$ =0.05 if the GMT ratio between the two groups is at least 1.93, and at least 90% power if the ratio is at least 2.14.

Table 3 below describes the statistical power to detect that the GMT ratio of an aQIVc formulation versus QIVc is significantly higher than 1 or higher than 1.5 at a two-sided 5% level of significance assuming 95 evaluable subjects per formulation and a standard deviation of 0.7 for the log10 titers.

	Power % to detect			
	Lower limit of the 95% CI of GMT	Lower limit of the 95% CI of		
Actual GMT ratio	ratio above 1	GMT ratio above 1.5		
2.00	83.86	23.08		
2.50	97.37	58.44		
3.00	99.67	83.86		
3.50	99.96	95.00		
4.00	100	98.65		

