### **Table 3 Power Calculations**

N=95 per group and two-sided alpha = 0.05

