### Analysis of binary endpoints

The number and proportion of subjects achieving the binary endpoints (seroconversion or HI titer >=1:40) will be summarized by assessment (Day 29), strain and vaccine group.

For each of the influenza vaccine strains and for each of the vaccine groups, summaries will include the associated two-sided 95% confidence intervals according to Clopper-Pearson.

The binary endpoints (i.e. seroconversion or titer  $\geq$ 1:40) will be compared between each aQIVc formulation and QIVc using the Miettinen and Nurminen method without adjustment for the age subgroup. The results will be presented as the difference in the percentage of subjects with 95% confidence intervals.

Additional supportive analyses may be done using generalized linear models with factors for vaccine group, age subgroup, pre-vaccination titer as well as previous vaccination history. Adjusted differences between vaccine groups with 2-sided 95% CI will be calculated based on the model and potential interaction effects will be examined.

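### The main aQIVc–QIVc difference in percentage with HI ≥1:40 at Day 29 is valid unadjusted, but gives up precision available from the pre-vaccination titer, which is only an optional covariate

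*SAP*

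**What the plan says.** Protocol 8.1.1.1 lists as a primary endpoint the percentage of subjects with HI titers at or above "1:40 at Day 1 and Day 29". It also names the between-group difference in that percentage at Day 29 as a derived variable for each strain.

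The plan treats the titer in two ways:

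- **GMT.** Protocol 8.4.2.2.3 and SAP 8.1 and 11.2 adjust the Day 29 log titer for log10 pre-vaccination titer, age subgroup and vaccination history. SAP 8.1 has both adjusted and unadjusted GMT ratios tabulated.
- **HI ≥1:40.** SAP 8.1 states that the main analysis of the binary endpoints "will not be adjusted for any of the covariates". Protocol 8.4.2.2.3 and SAP 11.2 use the Miettinen-Nurminen difference without age adjustment.

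Three passages describe an additional binary model:

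- SAP 8.1 allows one (*may*) with the two stratification factors only.
- SAP 11.2 is wider but still optional: "Additional supportive analyses may be done using generalized linear models with factors for vaccine group, age subgroup, pre-vaccination titer as well as previous vaccination history".
- Protocol 8.4.2.2.3 commits (*will*) to an exploratory model with antigen and MF59 levels and "adjustment for age and previous vaccination history using a generalized linear model for binary data". Pre-vaccination titer is not listed.

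Blood is drawn from all subjects on Day 1. The FAS definition (SAP 7.3) requires Day 1 and Day 29 immunogenicity data, and the PPS is a subset of the FAS.

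**The concern.** HI ≥1:40 is an absolute threshold, not a change from baseline. A subject already at or above 1:40 before vaccination is likely to count as a success whichever vaccine is given. The Day 1 titer is therefore the natural prognostic covariate, and leaving it out makes the interval wider than the data require.

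All seven formulations are compared with a single QIVc arm of about 95 evaluable subjects. If that arm happens to start high or low, all seven unadjusted differences move in the same direction. SAP 1 says the results will be used to select the formulation for Phase 3, so interval width and the apparent size of each difference matter even without formal tests.

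The Day 1 percentages will be tabulated, so an imbalance would be visible, but the plan fixes no response to it. Because the adjusted model is optional and its covariates differ between sections, whether and how to adjust could be decided after the data are seen.

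**Working it through.** **Inputs from the documents.** SAP Table 3 gives "N=95 per group and two-sided alpha = 0.05". The 95 follows from 100 randomised per arm and 5% non-evaluable: 100 × 0.95 = 95. For the SD, SAP 5 says "it is assumed that the within group standard deviations for the log10 HI titers for all strains are about 0.7 or lower".

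**The plan's own power figures.** These concern the GMT ratio; no power is given for HI ≥1:40.

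- SE of the log10 difference = 0.7 × √(2/95) = 0.1016.
- At a true ratio of 2.0, the noncentrality against 1 is log10(2.0)/0.1016 = 2.96, and against 1.5 it is log10(2.0/1.5)/0.1016 = 1.23.
- A two-sample noncentral t with 188 df gives 83.86% and 23.08%, as printed. Every other entry in the table also reproduces.
- At ratios 1.93 and 2.14 power is 79.9% and 89.9% (t), or 80.3% and 90.2% (normal approximation).

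The power table is sound and is not affected by this point.

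**Inputs not in the documents, so assumed.** The baseline-to-Day 29 correlation r is set at 0.3, 0.5 and 0.7. The percentages with HI ≥1:40 (QIVc vs aQIVc) are set at 50 vs 65, 70 vs 85 and 85 vs 95.

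**Simulation.** There were 4,000 trials per scenario with 95 per arm. A Day 29 log titer correlated with baseline was cut at the threshold. Two estimators were compared: the raw difference in proportions, and the difference standardised over the sample from a logistic model with arm and baseline log titer. Stratified randomisation was not simulated.

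| r | Variance, adjusted ÷ unadjusted | Variance cut | Unadjusted subjects per arm giving the same precision (95 ÷ ratio) | Move in the unadjusted difference per 1-SD chance baseline imbalance |
|---|---|---|---|---|
| 0.3 | 0.956–0.974 | 3–4% | 98–99 | 0.8–1.6 points |
| 0.5 | 0.852–0.904 | 10–15% | 105–111 | 1.3–2.7 points |
| 0.7 | 0.677–0.810 | 19–32% | 117–140 | 1.7–4.0 points |

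A 1-SD imbalance here is √(2/95) = 0.145 baseline SDs between two arms. The two estimators agreed in mean to within 0.001 in every scenario, so the quantity estimated does not change.

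**In interval terms, for 50% vs 65%.**

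- Unadjusted SE = √[(0.50 × 0.50 + 0.65 × 0.35)/95] = 0.0709, so the 95% half-width is 1.96 × 0.0709 = 13.9 points.
- Multiplying by √0.956, √0.852 and √0.677 gives 13.6, 12.8 and 11.4 points for r = 0.3, 0.5 and 0.7.

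**Check on the titer scale.** A second simulation (2,000 trials per scenario) used log10 titers with SD 0.7, values floored at 5, an assumed baseline GMT of 20, a QIVc Day 29 GMT of 80 and a GMT ratio of 2.0. The implied Day 29 percentages are Φ(log10(80/40)/0.7) = 67% and Φ(log10(160/40)/0.7) = 81%. The variance ratios were 0.96, 0.87 and 0.72, in line with the table.

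**The case against.** The strongest reply is that this is a preference and not an error. The unadjusted difference is a standard estimator, openly chosen and stated in both documents. Baseline is also handled in several other places: the GMT ratio is adjusted for it; seroconversion and GMFI use each subject's own Day 1 value; Day 1 percentages and reverse cumulative curves are shown by group; randomisation is stratified by age and vaccination history; and SAP 11.2 already names almost the model asked for here. The study is descriptive, with no hypothesis tests.

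Most of that stands, and it limits the point to precision and pre-specification. What it leaves open is that the one baseline-adjusted analysis of this endpoint is optional and appears in only one of three covariate lists.

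A reader might infer more than the documents support:

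- **That the unadjusted result is biased.** It is not; the simulated means agree.
- **That the SAP contradicts itself.** Sections 8.1 and 11.2 are both permissive sentences that differ in their covariates. They need aligning but do not conflict.
- **That adjustment removes the baseline shift.** About 68–97% of the variance of the difference remains.
- **That Day 29 results could be distorted by some 7 points.** If 40% had baseline HI ≥1:40, √(2 × 0.4 × 0.6/95) = 7.1 points is the SE of the Day 1 difference. The Day 29 effect of a 1-SD imbalance in baseline titer is 0.8–4.0 points under the assumptions above.
- **That this endpoint decides the formulation.** It is one of several unranked primary endpoints, and no selection rule is given.

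**Conclusion.** The concern holds as a modest, nearly cost-free gain in precision. The main comparison of HI ≥1:40 at Day 29 is valid, but it does not use a baseline value that every analysed subject has and that the plan already uses for the GMT.

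The size depends on a correlation and on response rates that the documents do not give. The variance reduction is negligible at r = 0.3 (3–4%), useful at r = 0.5 (10–15%) and material at r = 0.7 (19–32%). These figures are towards the upper end, because stratification by age and vaccination history already removes some baseline imbalance and was not simulated. The effect is on interval width and on how stable the seven differences look against the shared QIVc arm, not on any formal test. The calculation covers Day 29 HI ≥1:40 only; no claim is made for seroconversion or Day 181.

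**What to change.** 1. **SAP 8.1 and 11.2.** For HI ≥1:40 at Day 29, state that a binary regression *will* be fitted per strain with vaccine group, log10 pre-vaccination titer, age subgroup and vaccination history. Standardise it over the analysis set to give each aQIVc–QIVc risk difference with a 95% CI.
2. **Keep the unadjusted Miettinen-Nurminen difference beside it**, as is already done for adjusted and unadjusted GMT ratios.
3. **Give the same covariate list in 8.1 and 11.2.**
4. **Protocol 8.4.2.2.3.** Keep the antigen/MF59 binary model as the separate exploratory dose-response analysis, and add log10 pre-vaccination titer to its covariates.
5. **State a fallback** for a strain in which nearly all subjects reach 1:40, for example a penalised fit or the unadjusted difference alone.

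The cost is a few sentences of SAP text and one further model-based analysis per strain. No additional data or samples are needed, and because the analysis sets already require Day 1 data, adjustment should cost no subjects.

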### 8.2 Handling of Dropouts, Missing Data

The distribution of subjects with reasons for missing immunogenicity values will be described by vaccine group. Key baseline characteristics, such as age and previous vaccination history, will be compared between the subjects with immunogenicity values and those who have missing data. For immunogenicity data, it may be reasonable to consider missing immunogenicity values as missing completely at random (MCAR), i.e., not informative.

Therefore, the immunogenicity analysis will comprise a complete case analysis only, without introducing any bias.

Solicited adverse events are collected using electronic diaries from Day 1 to Day 7 postvaccination. If no data have been recorded for all 7 days, the assessment is considered missing and excluded from the safety analysis. In case, at least one day is filled in but other days are missing the presence or absence of the event will be based on the available data. If more than 5% of the subjects have incomplete diary data, additional tables for solicited adverse events will be created based on complete diary card data. The number of days and number of subjects with missing data will be tabulated by treatment group.

26 Augustus 2021 Final Version 2.0

### 8.3 Multicenter Studies

Stratification is used on two important factors related to the immunogenicity endpoints: age and previous vaccination history. These factors will be included in the statistical model. Centers will not be included in the statistical analysis, but countries will be considered in the sub-group analyses.

### 8.4 Multiple Comparisons and Multiplicity

This a phase 2, exploratory study and no adjustment will be applied for multiple endpoints and multiple comparisons.

### 8.5 Immunogenicity/Safety/Other Subsets

Not applicable.

# 8.6 Subgroups

All analyses (safety and immunogenicity) will be done by the age subgroups  $\geq$ 50-64 years or  $\geq$ 65 years.

Unadjusted and adjusted immunogenicity analysis of the GMTs will be performed by the following subgroups:

- Influenza vaccination history previous 3 years as yes and no, where we excluding this factor in the analysis model;
- Comorbidity risk (yes/no) defined as the Comorbidity Risk Score (by Hak et al.) < 50 (comorbidity risk = no) or ≥50 (comorbidity risk = yes);
- Sex;
- Country;
- Pre-vaccination status HI or MN < 1:10 (or LLOQ) and HI or  $MN \ge 1:10$  (or LLOQ)...

The adjusted GMT subgroup analysis will not be conducted if , the number of subjects in a subgroup category is less than 10% of the total population.

Exploratory interaction analyses may be conducted to support consistency or lack of consistency of the results among the subgroups.

#### 8.7 Data Transformation

Distributions of antibodies are generally skewed to the right and approximately log-normally distributed. Therefore, prior to any statistical analysis that assumes normally distributed observations, antibody titers will be log10-transformed. GMTs and their 95% CIs will be then computed by exponentiating (base 10) the means and 95% CIs of the log10 transformed titers.

#### 8.8 Derived and Computed Variables

#### **Demographics**

In the case that Age and/or Body Mass Index must be recomputed by standard software

Age will be calculated in years using the following formula:

Integer [(Date of Visit 1 – Date of Birth + 1) / 365.25]

Body Mass Index  $(kg/m^2)$  will be calculated using the following formula:

Mass (kg) / Height (m^2)

The total Comorbidity Risk Score will be derived by the sum of all scores (see protocol appendix 1). The total Comorbidity Risk Score will be categorized as a score < 50 or  $\ge 50$ .

#### **Immunogenicity**

Values below the lower limit of quantification will be set to half that limit. Values above the upper limit of quantification will be set to the value of this upper limit.

**Seroconversion** based on **HI** antibodies is defined as binary variable for subjects with non-missing values pre-vaccination- and post-vaccination as:

= 1, if seroconverted (defined as  $a \ge 4$ -fold increase in titer post-vaccination in those with prevaccination titer above the LLOQ (1:10), or a post-vaccination titer  $\ge 1:40$  for subjects with prevaccination titer below the LLOQ (1:10))

= 0, otherwise

**Seroconversion** based on **MN** antibodies is defined as binary variable for subjects with nonmissing values pre-vaccination- and post-vaccination as:

26 Augustus 2021 Final Version 2.0

= 1, if seroconverted (defined as a  $\geq$  4-fold increase in titer post-vaccination in those with prevaccination titer above the LLOQ, or a post-vaccination titer  $\geq$  4 times the LLOQ for subjects with pre-vaccination titer below the LLOQ

= 0, otherwise

Fold increase is defined as the post-vaccination titer divided by the pre-vaccination titer.

#### **Geometric Mean Titer**

The GMT will be calculated using the following formula:

$$10^{\left\{\frac{\sum\limits_{i=1}^{n}\log_{10}(t_i)}{n}\right\}}$$

where  $t_1, t_2, ..., t_n$  are *n* observed immunogenicity titers. The 95% confidence intervals for GMT will be calculated as  $10^{\{M-t_{0.975,n-1}SE\}}$ ,  $10^{\{M+t_{0.975,n-1}SE\}}$ ; where M and SE are the means and standard error of logarithm base 10-transformed titers, respectively.

### **Solicited Adverse Events**

For details see Section 13.2.

### **Unsolicited Adverse Events**

All adverse events will be characterized according to the date of occurrence related to the vaccination. If the start date is before the date of injection of study vaccine or indicated as on injection day but before injection, these events will not be considered as unsolicited adverse events and mapped to the medical history.

Note: If an adverse event start date is missing or unknown and no indication is provided on the timing, the adverse event will be considered as unsolicited adverse event.

When start and/or end dates of an adverse event are only partially known, adverse events will be categorized as unsolicited adverse event unless the partial end date is before the vaccination date.

All unsolicited adverse events emergent will be categorized as occurring during the treatment period of 28 days following vaccination (period Day 1 to Day 29) based on the start date. If start date is missing, events will be counted as yes during the period of 28 days following vaccination.

26 Augustus 2021 Final Version 2.0

The **maximum event severity** is the greatest severity associated with a preferred term (PT) for a reported adverse event according to the following order: Mild < Moderate < Severe.

**Vaccination-related Adverse Events** are those for which the cause has been evaluated by the investigator, and recorded as possibly related, probably related or unknown/ missing.

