# 7 ASSESSMENTS

## 7.1 Safety Assessments

The measures of safety used in this study are routine clinical procedures. They include a close vigilance for and stringent reporting of selected local and systemic AEs routinely monitored in vaccine studies as indicators of reactogenicity.

An AE is defined as any untoward medical occurrence in a subject or clinical investigation subject administered a pharmaceutical product at any dose that does not necessarily have to have a causal relationship with this treatment. Therefore, an AE can be any unfavorable and unintended sign (including an abnormal laboratory finding, for example), symptom, or disease temporally associated with the use of an investigational product, whether or not considered related to the investigational product. This definition includes intercurrent illnesses or injuries and exacerbation of pre-existing conditions.

The period of observation for AEs extends from the time immediately after the subject has received the study vaccine until he or she completes the specified safety follow-up period at the end of the influenza season. When a subject terminates the study early, the period of observation will stop as well. Events occurring prior to receiving study vaccine/product will be documented as medical history and recorded within the source document. Adverse events

are collected as either solicited or unsolicited; solicited events are derived from organized data collection systems, such as Subject eDiaries or interviews.

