#### 8.1.1.2 Primary Safety Endpoints

- Solicited local or systemic AEs for 7 days following vaccination (Day 1 through Day 7), based on the subject reported data (eDiary).
- Severe solicited local or systemic AEs for 7 days following vaccination (Day 1 through Day 7), based on the subject reported data (eDiary).
- Unsolicited AEs for 28 days following vaccination (Day 1 to Day 29).
- SAEs, MAAE, AEs leading to withdrawal from the study, AESIs for 28 days after vaccination (Day 1 to Day 29).

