#### 8.4.3.1.3 Analysis of Unsolicited Adverse Events

This analysis applies to all AEs occurring during the study, judged either as probably related, possibly related, or not related to vaccination by the investigator, recorded in the AE eCRF, with a start date on or after the date of vaccination. The original verbatim terms used by

investigators to identify adverse events in the eCRFs will be mapped to preferred terms using the MedDRA dictionary.

The adverse events will then be grouped by MedDRA preferred terms into frequency tables according to system organ class. All reported AEs, as well as AEs judged by the investigator as at least possibly related to study vaccine, will be summarized according to system organ class and the preferred term within system organ class. These summaries will be presented by the vaccination group and by the interval of study observation (Day 1 to Day 29, Day 30 to end of study). When an AE occurs more than once for a subject, the maximal severity and strongest relationship to the vaccine group will be counted.

Separate summaries will be produced for the following categories

- AEs
- SAEs
- AEs that are possibly or probably related to the vaccine
- SAEs that are possibly or probably related to the vaccine
- AESIs
- MAAEs
- AEs leading to withdrawal

Data listings of all adverse events will be provided by subject.

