#### 13.4 Unsolicited Adverse Events

This analysis applies to all AE's occurring during the study, judged either as probably related, possibly related, or not related to vaccination by the investigator, recorded in the AE eCRF.

The original verbatim terms used by investigators to identify adverse events in the eCRFs will be mapped to preferred terms using the MedDRA dictionary.

The adverse events will then be grouped by MedDRA preferred terms into frequency tables according to system organ class. All reported AEs, as well as AEs judged by the investigator as at least possibly related to study vaccine, will be summarized according to system organ class and the preferred term within system organ class. These summaries will be presented by vaccination group. When an AE occurs more than once for a subject, the maximum severity and strongest relationship to the vaccine group will be counted.

The assignment to safety follow-up time intervals will be done by day of onset and not by days ongoing/persisting.

26 Augustus 2021 Final Version 2.0

The summaries will be presented by period of onset (Day 1 to Day 29, Day 30 to end of study or Day 1 to end of study). An overview summary will be created by time -period with number and % of subjects with the following categories:

- AE
- AE by maximum severity
- Related (i.e. at least possible) AE
- SAEs
- Related SAEs
- AESIs
- MAAEs
- AEs leading to withdrawal from study
- Deaths.

The following summaries will be produced by SOC and Preferred Term and by time-period (Day 1 to Day 29, Day 30 to end of study or Day 1 to end of study):

- AEs
- AEs by maximum severity
- AEs that are possibly or probably related to the vaccine
- SAEs
- SAEs that are possibly or probably related to the vaccine
- AESIs
- MAAEs
- AEs leading to withdrawal
- Deaths.

Data listings of all adverse events will be provided by subject. In addition, adverse events in the categories above will be provided as listed data.

All tables will be produced overall and by age subgroup.

Print Date (Local): 26-Aug-2021 16:31:00

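### For partly dated adverse events, SAP 8.8 tests only the end date, so an event known to have begun before vaccination can be kept as unsolicited; it also has no rule placing partial start dates in a period

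*SAP*

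**What the plan says.** SAP 8.8, Unsolicited Adverse Events, gives four rules.

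1. **Known early start.** "If the start date is before the date of injection of study vaccine or indicated as on injection day but before injection", the event is not an unsolicited adverse event and goes to medical history.
2. **Missing start, status.** "If an adverse event start date is missing or unknown and no indication is provided on the timing", the event is treated as unsolicited.
3. **Partial start and/or end, status.** Here "adverse events will be categorized as unsolicited adverse event unless the partial end date is before the vaccination date".
4. **Period.** Events are placed in the 28-day treatment period by start date. "If start date is missing, events will be counted as yes during the period of 28 days following vaccination".

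The surrounding text bears on these rules. Protocol 8.4.3.1.3 limits the unsolicited analysis to events "with a start date on or after the date of vaccination". Protocol 7.1 says "Events occurring prior to receiving study vaccine/product will be documented as medical history". SAP 13.4 repeats much of Protocol 8.4.3.1.3 but leaves out the start-date condition, and adds that "The assignment to safety follow-up time intervals will be done by day of onset and not by days ongoing/persisting". Unsolicited events in Day 1 to Day 29 are a primary safety endpoint (Protocol 8.1.1.2). SAP 16 does not list the date rules as a change to the planned analysis.

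**The concern.** Onset decides whether an event belongs in this analysis, and in which period. Rule 3 turns on the end date instead. An end-date test suits concomitant medication, where use continuing past vaccination is what counts, and SAP 8.8 uses one there. For adverse events, it lets a condition with a known earlier onset stay in the unsolicited tables because it had not ended by vaccination.

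Rule 4 has a related defect. Rule 2 applies its default only when nothing indicates the timing, but the period sentence carries no such limit. A record with no start date but other recorded information on onset would still be counted in Day 1 to Day 29.

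Partial start dates have no period rule at all. Two programmers working from the same text could produce different tables for a primary safety endpoint in a study that compares eight arms to choose a Phase 3 formulation.

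**Working it through.** The plan gives no figure to reproduce here, because the point concerns a classification rule. I applied the four rules literally to seven date patterns. The vaccination date of 15 April 2021 is an illustrative assumption; Day 29 is then 13 May 2021.

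| Start | End | Rule 1 | Rules 2 to 4 |
|---|---|---|---|
| 10 Mar 2021 | 1 May 2021 | excluded | do not apply |
| 10 Mar 2021 | May 2021 (partial) | excluded | rule 3 keeps it: **direct conflict** |
| Feb 2021 (partial) | 1 May 2021 | excluded only if rule 1 covers partial dates | rule 3 keeps it: **wrong as written** |
| Feb 2021 (partial) | Mar 2021 (partial) | excluded only if rule 1 covers partial dates | rule 3 excludes it |
| Apr 2021 (partial) | 1 May 2021 | silent, onset ambiguous | rule 3 keeps it: reasonable default |
| missing, first reported Day 181 | missing | silent | rule 4 counts it in Day 1 to Day 29 |
| Aug 2021 (partial) | missing | silent | rule 3 keeps it; **no period rule** |

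- **Second row.** Both rules apply and give opposite answers, so a program cannot satisfy both.
- **Third row.** Onset is before vaccination on any day in February. Under Protocol 7.1 and 8.4.3.1.3 the event falls outside the analysis, yet rule 3 retains it. SAP 13.4 has no later filter to remove it.
- **Last row.** The start is partial, not missing, so rule 4 does not reach it. Onset is after Day 29 on any day in August, but no sentence says so.

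**Scale.** The planned arm size is about 100 (SAP 3.1), so one record is 1/100 = 1 percentage point. With Clopper-Pearson 95% intervals:

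- 0/100 is 0% (0 to 3.62%); 1/100 is 1% (0.03 to 5.45%).
- 20/100 is 20% (12.67 to 29.18%); 21/100 is 21% (13.49 to 30.29%).

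The 20% rate is illustrative. The documents give neither an expected event rate nor a rate of incomplete dates, so the number of affected records cannot be calculated.

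**The case against.** The case for leaving the text alone has several parts.

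**Rule 1 may already cover it.** A start month wholly before vaccination can fairly be read as a start date before injection. That reading rescues the third row, but it leaves two rules in open conflict and does nothing for the second row.

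**Upstream controls make such records rare.** Events before vaccination are documented as medical history (Protocol 7.1), and a pre-existing condition is reported as an adverse event only if it worsens (Protocol 7.1.4). Queries and data cleaning should resolve many incomplete dates. This stands, and it is why the expected effect is small.

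**The safety analysis is descriptive and all events are listed by subject.** This also stands: no test or power figure is touched, and a misdated record remains visible in the final listings.

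A reader might draw three stronger conclusions, none of which the documents support.

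- *Events first reported after Day 29 are put in the wrong period.* The date of first report is not the date of onset. The Day 29 visit window is -7/+3 days, so the visit may fall on Day 22 (29 - 7). An event starting on Days 23 to 29 could then first be reported at Day 91. For a missing start date with no other onset information, the Day 1 to Day 29 default is conservative and overrides no known fact.
- *Pre-existing conditions are directed into the primary 28-day endpoint.* Rule 3 settles unsolicited status only. No sentence places a partial pre-vaccination start in Day 1 to Day 29; that step is unspecified.
- *The rule makes the Day 29 and full-study reports disagree.* The first analysis uses data from Visits 1 to 3. Any late-reported event with a known onset in Day 1 to Day 29 would also change the later count, so a difference is not peculiar to this rule.

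**Conclusion.** The point holds. As written, the partial-date rule misclassifies events whose known start is wholly before vaccination, and it contradicts both the opening rule of the same subsection and Protocol 8.4.3.1.3. The missing condition in rule 4 and the absence of a period rule for partial starts are gaps in the same derivation.

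The expected effect is small: 1 percentage point per record in an arm of about 100. It matters most in rare categories, where one record turns 0% into 1%. This rests on the planned arm size and on a literal reading of rule 3; the frequency of incomplete dates is unknown. The worst-case default remains sound wherever the known parts of the dates leave onset ambiguous.

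**What to change.** Amend SAP 8.8 as follows.

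- **(a)** A full or partial start date that lies wholly before vaccination maps the event to medical history, whatever the end date.
- **(b)** A partial start date that lies wholly after Day 29 is assigned to Day 30 to end of study.
- **(c)** A missing or ambiguous start date keeps the Day 1 to Day 29 default, unless recorded information on onset places the event after Day 29. State that the date of first report alone is not such information.

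Restoring the start-date condition of Protocol 8.4.3.1.3 in SAP 13.4 would bring the two documents into line. The cost is a few lines of text and a small change to the date-derivation program, with no new data collection.
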